1 INTRODUCTION

1.1 Disease background and current treatment modalities

Despite differences among countries, the incidence and prevalence of allergic rhinitis and asthma are increasing worldwide. AR/C affects between 10 to 30% of all adults and up to 40% of children (Pawankar et al. 2011). Sensitisation rates to 1 or more common allergens among school children are estimated to be 40%-50% (Pawankar et al. 2011). Tree pollen allergy is common across central and northern Europe and North America and is commonly caused by pollen from the birch and related trees, also commonly referred to as the birch homologous group (hereafter referred to as "birch group"). This group currently includes birch, alder, hornbeam, hazel, beech and oak (Lorenz et al. 2009), although more species may be included when additional data on cross-reactivity and allergen homology becomes available (Heath et al. 2015). AIT guidelines recommend treating allergic patients with AIT using a representative allergen within a homologous allergen group (Cox et al. 2011; EMEA 2008).

The trees in the birch group are characterised by having Bet v 1 homologous allergens with a high level of structural sequence identity, leading to extensive cross-reactivity at the immune response level. Thus, people who are sensitised to pollen from one of the trees often also experience symptoms in response to pollen from other members of the birch group. Sensitisation to Bet v 1 has been estimated up to 24% in adults (Burbach et al. 2009; Chan-Yeung et al. 2010), and between 14-16% in children (Schmitz et al. 2013; Stemeseder et al. 2017). The broad cross-reactivity and sequential pollen seasons of birch related allergens prolong the period of allergic symptoms for people with allergy to birch. In previous clinical trials conducted by ALK in Europe and North America with the SQ tree SLIT-tablet, more than 90% of participants with AR/C induced by birch pollen were also sensitised to alder and hazel (Biedermann et al. 2019a). Furthermore, Jantunen et al. showed that 95% of patients diagnosed with birch pollen allergy presented with allergic symptoms during the alder season (Jantunen et al. 2012). Cross-reactivity of birch pollen allergens also extends to plant food allergens, resulting in the pollen food syndrome (Biedermann et al. 2019b).

Treatment options for AR/C include allergen avoidance, symptomatic medications such as antihistamines and corticosteroids, and AIT (Bousquet et al. 2008). Avoidance of pollen is difficult to achieve in a normal daily life, and symptom-relieving medication is widely used, however it does not offer causal treatment of the allergic disease and up to 44% of patients on optimal symptom-relieving medication report poor or only partial symptom control (Valovirta et al. 2008). AIT is the only available treatment modality that can modify the natural course of the allergic disease by induction of tolerance (Bousquet et al. 2008). The use of pollen extract for AIT is well-known, both in SCIT formulations (Blumberga et al. 2011; Bousquet et al. 1998a; Lang & Hawranek 2006; Winther et al. 2000a; Winther et al. 2000b) and as SLIT-tablets or drops (Demoly et al. 2016; Durham et al. 2012).

1.2 Stage of development

The SQ tree SLIT-tablet is a once daily fast-dissolving pharmaceutical formulation (oral lyophilisate) containing standardised allergen extract of white birch (*Betula verrucosa*) for AIT of seasonal AR/C induced by pollen from birch and trees belonging to the birch homologous group.

Clinical trial protocol	Date:	24-May-2020	
EudraCT No: 2020-004372-17 CONFIDENTIAL	Status: Page:	5.0 Final 25 of 99	ALK

The SQ tree SLIT-tablet is approved in 17 European countries for treatment of adults with moderate to severe AR/C induced by the pollen from the birch homologous group, while in Switzerland this approval encompasses adults and adolescents (12-17 years old). In Canada, the SQ tree SLIT-tablet is approved for treatment of adults with moderate to severe AR/C induced by pollen from birch, alder and/or hazel.

The clinical development programme for the SQ tree SLIT-tablet comprises 4 phase I-III randomised, double-blind, placebo-controlled clinical trials in Europe and North America. The clinical efficacy of the SQ tree SLIT-tablet was confirmed in a phase III in-field trial (TT-04) including both adults (≤65 years old) and a small group of adolescents (12-17 years old) in Europe. The results demonstrated a statistically significant improvement with the SQ tree SLIT-tablet treatment compared to placebo for the average TCS during the BPS, the TPS and the AHPS. The average DSS and the average DMS (both components of the total combined score) also showed statistically significant improvements compared to placebo during the BPS, TPS and AHPS. A pre-specified analysis comparing the treatment effect in the adolescent and adult populations did not show a statistically significant difference in treatment effect between the 2 age groups.

The clinical relevance of the cross-reactivity between birch and oak was demonstrated in a phase II environmental exposure chamber trial (TT-03) and was further investigated (post-hoc) in the oak pollen season in the phase III in-field trial TT-04. Significant treatment effects were seen after exposure to birch as well as oak pollen both in the environmental exposure chamber and post-hoc in the phase III clinical field trial.

The SQ tree SLIT-tablet was generally well-tolerated with a safety profile characterised by frequent but transient local allergic events in the first few days of treatment, primarily occurring in or around the mouth and throat (e.g. pruritus, irritation, sensation changes, discomfort, swellings, and pain), that were typically assessed as mild or moderate in intensity. Severe allergic reactions were uncommon. Overall, the SQ tree SLIT-tablet was well-tolerated in subjects with tree pollen allergy with no major safety concerns detected. Finally, the safety profile was generally similar across age subgroups (adolescent vs adult).

1.3 Trial rationale

The prevalence of allergy induced by birch and cross-reactive tree pollen in children and adolescents in the general population is 14-16% (Schmitz et al. 2013; Stemeseder et al. 2017). A substantial number of these children and adolescents do not reach sufficient symptom control when treated with pharmacotherapy (antihistamines/steroids) (Meltzer et al. 2009). Furthermore, most subjects with birch pollen allergy are poly-sensitised to pollen from related trees and may experience symptoms to early and/or late flowering trees in the birch homologous group. Thus, the symptom burden extends beyond the birch season and therefore this trial will evaluate symptoms and medication use during the birch pollen season and also during the alder/hazel, and oak pollen seasons.

The SQ tree SLIT-tablet has been demonstrated in adults with AR/C induced by pollen from the birch group to be efficacious in reducing the symptoms of AR/C, and has an acceptable safety and tolerability profile with few reported serious AEs (SAEs), of which none were assessed as related to the SQ tree SLIT-tablet (12 SQ-Bet). Furthermore, the TT-04 trial did not provide evidence that the efficacy and safety profile of the SQ tree SLIT-tablet differs between adults and adolescents. The SQ tree SLIT-tablet has yet to be studied in children <12 years old.

Clinical trial protocol	Date:	24-May-2020	
Trial ID: TT-06	Version:	3.0	
EudraCT No: 2020-004372-17	Status:	Final	
CONFIDENTIAL	Page:	26 of 99	

Currently, there is no approved SLIT product in Europe or North America for the treatment of allergy in children with a history of AR/C symptoms induced by pollen from the birch group and treatment in adolescents is only authorised in Switzerland.

Therefore, there is an unmet clinical need to develop a treatment that can expand the treatment options for children and adolescents suffering from AR/C induced by pollen from the birch group.

This trial is a part of the phase III development programme for the SQ tree SLIT-tablet. The purpose of this trial is to evaluate the efficacy and safety of the SQ tree SLIT-tablet in paediatric subjects (5 through 17 years of age) with persistent moderate to severe AR/C (with or without asthma) induced by pollen from the birch group despite being treated with symptom-relieving medication.

1.4 Benefit-risk assessments

The SQ tree SLIT-tablet provides an alternative formulation and mode of administration of immunotherapy that expands the treatment options for children suffering from AR/C induced by pollens from the birch group. The orodispersible dosage form is ideally suited for the treatment of children as it is easy to administer, and the rapid dispersion makes it difficult to spit out or aspirate (EMEA 2006).

The SQ tree SLIT-tablet is an effective treatment for adult patients for whom AIT is indicated and has an acceptable safety profile in this population. In contrast to SCIT treatments, the SQ tree SLIT-tablet does not require up- or down-titration and allows for at-home dosing after administration of the first dose in a health care setting under the supervision of a physician with experience in the treatment of allergic diseases.

In the current trial, the SQ tree SLIT-tablet may show an effect on symptom relief and reduce the use of symptom-relieving medication in children as well. Thus, subjects on active treatment in the trial may receive a direct benefit of access to a new treatment that is not yet commercially available.

All subjects participating in the trial will have access to symptom-relieving medication and will receive expert medical care. Their participation will contribute to the development of the new treatment for children suffering from allergy induced by pollen from the birch group.

The SQ tree SLIT-tablet has been demonstrated to be well-tolerated and suitable for self-administration in adults. Typical adverse reactions are transient local reactions occurring within the first few days of treatment. These are expected in paediatric subjects as well. Other potential adverse reactions are class effects of AIT/SLIT and include acute worsening of asthma symptoms (exacerbation), EoE, anaphylactic reactions, and serious laryngo-pharyngeal reactions. However, these reactions are rare and are not expected to increase in the paediatric population.

Risks in this trial are manageable when the first SLIT-tablet is administered under physician supervision and with appropriate education of the subject and parent/guardian about symptoms and signs of severe allergic reactions. There is no expectation of an increased safety risk for children enrolled in this trial compared with that observed in adults in previous tree pollen trials.

Clinical trial protocol	Date:	24-May-2020	
Trial ID: TT-06	Version:	3.0	
EudraCT No: 2020-004372-17	Status:	Final	
CONFIDENTIAL	Page:	27 of 99	

This is supported by similar safety profiles in adult and paediatric subjects treated with SLIT-tablets in grass pollen and ragweed pollen trials.

Based on the efficacy/safety trials of SQ tree SLIT-tablet in adults and a small group of adolescents, in addition to the results seen for grass and ragweed SLIT-tablet in both adults and children (ages 5 to 65 years), the benefit/risk assessment for conducting this paediatric trial of SQ tree SLIT-tablet is favourable.

Additional details regarding specific benefits and risks for subjects participating in this clinical trial may be found in the accompanying Investigators Brochure and Informed Consent documents.

1.5 Considerations regarding COVID-19

Participating in this trial, including receiving treatment with AIT, is not expected to increase subjects' risk of contracting communicable diseases, including COVID-19. The risk to subjects with asthma is considered unchanged as only subjects with well controlled mild to moderate asthma are included.

The COVID-19 situation and its impact on clinical trial conduct and activities will be continuously monitored by the Sponsor to ensure safety of subjects and trial staff. Local guidance requiring the use of personal protective equipment or other measures to ensure patient safety should always be followed. If regional circumstances related to COVID-19 change, local guidance should be followed.

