4.2 Exclusion criteria

Subjects are excluded from the trial if any of the following criteria apply:

- E1. Previously randomised in this trial.
- E2. Is participating or planning to participate in any other interventional clinical trial during the duration of this trial
- E3. A clinically relevant history of symptomatic seasonal AR/C caused by an allergen source, other than tree pollen from the birch homologous group, with a season overlapping the TPS
- E4. A clinically relevant history of symptomatic perennial AR/C caused by an allergen source such as animal hair and dander to which the subject is exposed during the TPS.
- E5. Asthma requiring high daily doses²³ of inhaled corticosteroids within 3 months prior to the randomisation visit
- E6. Any clinical deterioration of asthma (i.e. asthma exacerbation) that resulted in emergency treatment, hospitalisation or treatment with systemic corticosteroids within 3 months prior to randomisation

²⁰ If medical records are not available, verbal history from subject/parent/caregiver may be elicited at the Screening Visit and can be used to fulfil this criterion if documented in the subject study file by the investigator.

²¹ A positive SPT is defined in the SPT guideline. Briefly, a positive SPT is defined as a wheal size of ≥3 mm. If medication that could interfere with the SPT, according to prohibited and restricted medication table, has not been washed out, the SPT must be performed after the interfering medication has been washed out.

²² A positive specific IgE is defined as ≥IgE Class 2; ≥0.70 kU/L

²³ For acceptable/prohibited ICS doses see **Table 4** (for children) or **Table 5** (for adolescents)

Clinical trial protocol	Date:	24-May-2020	
Trial ID: TT-06	Version:	3.0	
EudraCT No: 2020-004372-17	Status:	Final	
CONFIDENTIAL	Page:	37 of 99	

- E7. Reduced lung function at randomisation defined as FEV₁ <70% of predicted value. For asthmatic subjects this is assessed on subject's usual asthma medication following at least a 6-hour wash-out of SABA.
 This criterion does not need to be fulfilled if the subject is <7 years old, cannot perform reproducible FEV₁ manoeuvres despite coaching and is not considered as having a diagnosis of asthma.

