- E8. SLIT treatment with pollen allergen extracts from birch and trees belonging to the birch homologous group for more than 1 month within the last 5 years. In addition, any SLIT treatment with birch pollen or a cross-reactive/homologous tree pollen allergen extracts within the previous 12 months.
- E9. SCIT treatment with pollen allergen extracts from birch and trees belonging to the birch homologous group reaching the maintenance dose within the last 5 years. In addition, any SCIT treatment with birch pollen or a cross-reactive/homologous tree pollen allergen extracts within the previous 12 months.
- E10. Ongoing treatment with any allergy immunotherapy product
- E11. Severe chronic oral inflammation
- E12. Any nasal or naso/oropharyngeal condition that could confound the efficacy or safety assessments (e.g. hypertrophy of the pharyngeal/palatine tonsils, clinically relevant nasal polyps, a history of paranasal sinus surgery or surgery of nasal turbinates)
- E13. A diagnosis of EoE
- E14. A history of chronic urticaria (>6 weeks) and/or chronic angioedema (>6 weeks) within the last 2 years prior to screening that in the opinion of the investigator may constitute and increased safety concern
- E15. A relevant history of systemic allergic reaction e.g. anaphylaxis with cardiorespiratory symptoms, generalised urticaria or severe facial angioedema that in the opinion of the investigator may constitute an increased safety concern
- E16. Any clinically relevant chronic disease incl. malignancy that in the opinion of the investigator would interfere with the trial evaluations or the safety of the subject
- E17. Active or poorly controlled autoimmune diseases, immune defects, immunodeficiencies, immunosuppression or malignant neoplastic diseases with current disease relevance
- E18. Immunosuppressive treatment (ATC code L04 or L01) within 90 days prior to the screening visit
- E19. Treatment with medications with potential impact on efficacy endpoints. For example:
 - Treatment with anti-IgE drugs within 130 days/5 half-lives of the drug (which ever longest) prior to randomisation
 - Treatment with antidepressant within 14 days prior to randomisation
 - Treatment with antipsychotic medications with antihistaminic effect within 7 days prior to randomisation
- E20. Treatment with an investigational drug within 30 days/5 half-lives of the drug (which ever longest) prior to screening

Clinical trial protocol	Date:	24-May-2020	
Trial ID: TT-06	Version:	3.0	

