Immunotherapy with any other allergen(s)	From visit 1 and until TC4
Inhaled, topical or oral nedocromil or cromolyn sodium	≤14 days before visit 4 and until TC4

²⁴Tricyclic antidepressants and MAOIs may potentiate the effect of adrenaline/epinephrine ²⁵Estimated equipotent doses (i.v. or p.o.); 20 mg Hydrocortisone = 5 mg Prednisolone = 5 mg Prednisone = 4 mg Methylprednisolone = 0.75 mg Dexamethasone (Liu et al, 2013)

Clinical trial protocol	Date:	24-May-2020
Trial ID: TT-06	Version:	3.0
EudraCT No: 2020-004372-17	Status:	Final
CONFIDENTIAL	Page:	43 of 99

Drug	Time window
Long-acting β_{2-a} gonist (LABA) monotherapy (low and medium dose ICS/LABA in combination are allowed).	From 30 days before visit 4 and until TC4
Leukotriene receptor antagonists (e.g. montelukast, zafirlukast)	From visit 1 and until TC4. If treatment has begun at least 30 days prior to visit 1 dose can be kept unchanged during trial.
Nasal or ocular decongestants	≤7 days before visit 4 and until TC4
SABA, unless provided as rescue medication in the trial	From visit 4 and until visit 6

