8.2.2 Asthma rescue medication

SABA (i.e. salbutamol inhaler, 100 mcg/puff) will be provided to subjects with asthma at visit 4 and at subsequent visits as necessary. The salbutamol inhaler should be used when necessary according to the label.

Other medications for asthma will not be provided or reimbursed. Subjects who are taking low or medium daily dose ICS alone or in combination with LABA for asthma management will be allowed

Clinical trial protocol	Date:	24-May-2020	
Trial ID: TT-06	Version:	3.0	/
EudraCT No: 2020-004372-17	Status:	Final	
CONFIDENTIAL	Page:	45 of 99	

to continue with the same medications during the trial. A subject must have been on a stable regimen (daily dose unchanged) for at least 4 weeks before randomisation (visit 2). Low and medium daily doses of ICS are defined in **Table 4** and **Table 5**.

If a subject requires additional asthma medications, the subject should follow recommendations regarding medication adjustments provided by his/her physician. Medication use should be recorded in the eCRF.

Table 4	Definition of low, medium and high dose ICS for subjects aged 5-11 years as
	defined by the modified GINA Guideline

Inhaled corticosteroid	Low daily dose (micrograms (µg))	Medium daily dose (micrograms (μg))	High daily dose (micrograms (μg))
Beclomethasone dipropionate (pMDI, standard particle, HFA)	100 – 200	>200 - 400	>400
Beclomethasone dipropionate (pMDI, extrafine particle*, HFA)	50 – 100	>100 - 200	>200
Budesonide (DPI)	100 - 200	>200 - 400	>400
Budesonide (nebules)	250 – 500	>500 - 1000	>1000
Ciclesonide (pMDI, extrafine particle*, HFA)	80	>80 –160	>160
Fluticasone furoate (DPI)	50		n.a.
Fluticasone propionate (DPI)	50 – 100	>100 - 200	>200
Fluticasone propionate (pMDI, standard particle, HFA)	50 – 100	>100 - 200	>200
Mometasone furoate (pMDI, standard particle, HFA)	100	200	>200

DPI: dry powder inhaler; HFA: hydrofluoroalkaline propellant; ICS: inhaled corticosteroid; n.a.: not applicable; pMDI: pressurised metered dose inhaler (non-cholofluorocarbon formulations).

* See product information.

Note: Dose delivery by method or modality other than those noted above must be equivalent **Source**: modified from GINA (GINA Executive Committee 2020)

Clinical trial protocol	Date:	24-May-2020	
Trial ID: TT-06	Version:	3.0	
EudraCT No: 2020-004372-17	Status:	Final	
CONFIDENTIAL	Page:	46 of 99	

Κ

Table 5Definition of low, medium and high dose ICS for subjects aged 12 years and

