9.2 Precautions in relation to first dosing

First intake of IMP should be at the clinic with a subsequent 30 minute observation period.

For subjects with severe oral inflammation (e.g. oral lichen planus, mouth ulcers or thrush), oral wounds or following oral surgery, including dental extraction, or following tooth loss, initiation of IMP treatment should be postponed to allow healing of the oral cavity.

For subjects with symptoms of or in treatment for upper respiratory tract infection, acute sinusitis, acute otitis media or other relevant infections, initiation of IMP treatment should be postponed until the condition has improved.

If first dosing is postponed, the first intake of IMP should still be at the clinic with a subsequent 30 minutes observation period.

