11.6 Medical history

The relevant medical history, including diseases present at trial entry and any allergy, urticaria, asthma, atopic dermatitis and OAS, must be recorded in the eCRF.

The asthma history should include a detailed description of all asthma exacerbations including information on visits to emergency rooms, hospitalisations and changes in asthma treatment during the past 2 years. Those subjects suspected of having a history of asthma must meet at least one of the following 4 criteria to be considered as having a diagnosis of asthma (and documented as such in the eCRF):

- At least one episode of wheeze, cough, shortness of breath or chest tightness and a change in FEV₁ ≥12% after β₂-agonist administration
- Recurrent wheeze with or without prolonged phase of forced exhalation observed at physical examination and an intake of asthma medication which resulted in a clinically relevant effect
- Wheezing with or without prolonged phase of forced exhalation observed at physical examination and a change in FEV₁ \geq 12% after β_2 -agonist administration
- Using asthma medication

The OAS history should include a description of food triggers and symptoms.

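### Section 1.5 says only well controlled asthma is enrolled, but no eligibility criterion checks current asthma control

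*Protocol*

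**What the plan says.** Section 1.5 of the protocol (COVID-19 considerations) states that "only subjects with well controlled mild to moderate asthma are included" and gives this as the reason why the risk to subjects with asthma is unchanged.

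Eligibility is set in sections 4.1 and 4.2. I4 admits children with or without asthma and attaches no condition on control. Three exclusions are specific to asthma:

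- E5: asthma needing high-dose ICS within 3 months before randomisation.
- E6: "Any clinical deterioration of asthma (i.e. asthma exacerbation) that resulted in emergency treatment, hospitalisation or treatment with systemic corticosteroids", again within 3 months before randomisation.
- E7: "Reduced lung function at randomisation defined as" FEV1 below 70% of predicted, measured on usual asthma medication after a SABA wash-out of at least 6 hours.

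E16 is a general criterion: "Any clinically relevant chronic disease incl. malignancy that in the opinion of the investigator would interfere" with trial evaluations or the subject's safety. Outside the list, Table 1 and section 8.2.2 require that any ICS dose has been unchanged for at least 4 weeks before visit 2.

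**The concern.** The sentence in 1.5 is an unqualified description of who is enrolled, and a safety conclusion is drawn from it. A reader would expect at least one criterion to deliver it. The asthma criteria are proxies: treatment intensity, recent severe events and lung function. A child can satisfy all of them while having poor day-to-day control, especially if under-treated.

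The stake is safety and the description of the population. Section 1.4 lists acute worsening of asthma among the class effects of this kind of immunotherapy, and all dosing after the first tablet is at home. Section 1.3 says the tablet has yet to be studied in children under 12. SAP section 8.4 lists only asthma status among the baseline characteristics, so the report could not show whether the children with asthma were well controlled at entry.

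**Working it through.** No sample-size, power or error-rate figure bears on this point, so the check is a reading of the eligibility list against the statement in 1.5.

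**Step 1: count the criteria.** I1 to I8 give 8 and E1 to E24 give 24, so 8 + 24 = 32. The numbering is complete. Asthma-specific: E5, E6 and E7, so 3 of 32. Criteria that test current symptoms, night symptoms, activity limitation or reliever use: 0 of 32.

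**Step 2: run a test case through them.** Take a child with asthma who has frequent symptoms and frequent SABA use, takes no ICS or a stable low dose, has FEV1 of 72% predicted, and has had no emergency treatment, hospitalisation or systemic corticosteroids in the past 3 months.

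| Criterion | What it tests | Result for this child |
|---|---|---|
| I4 | Birch-pollen AR/C history; asthma allowed | Met |
| E5 | High-dose ICS within 3 months | Not triggered (none or low dose) |
| E6 | Exacerbation with emergency care, hospitalisation or systemic steroids within 3 months | Not triggered |
| E7 | FEV1 <70% predicted | Not triggered (72% ≥ 70%) |
| E16 | Investigator opinion on any chronic disease | Discretionary; asthma not mentioned, no standard set |

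The child is not well controlled and meets every asthma-specific criterion.

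**Step 3: look for a check elsewhere in the protocol.**

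- *ICS stability (Table 1, 8.2.2).* An unchanged dose shows a stable prescription, not control. The rule does not bear on a child taking no ICS, and no minimum controller treatment is required.
- *Reliever use (Table 1).* The row "SABA, unless provided as rescue medication in the trial" applies from visit 4 until visit 6. Reliever use at entry has no limit.
- *Asthma history (11.6).* "The asthma history should include a detailed description of all asthma exacerbations including information on visits to emergency rooms", hospitalisations and treatment changes over 2 years. Current symptoms and reliever frequency are not requested.
- *Visits 1 and 2 (section 10, Table 6).* No asthma-control assessment is listed.
- *First dose (9.2).* It is postponed for oral conditions and infections ("For subjects with symptoms of or in treatment for upper respiratory tract infection, acute sinusitis, acute otitis media" or other relevant infections). Symptomatic asthma is not a reason to postpone.
- *After entry (5.1).* Control appears only here, as a reason to stop treatment if asthma becomes hard to control.

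Nothing outside the eligibility list fills the gap.

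**The case against.** The strongest reply is that 1.5 is background text about communicable disease and is not an eligibility rule. The benefit-risk argument in 1.4 does not depend on it. It relies on a supervised first dose, education, and similar safety in adults and children in the grass and ragweed tablet trials, and it calls these reactions rare and not expected to increase in children. On this view, editing one sentence is enough.

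There are also real safeguards:

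- Under E16 a physician experienced in paediatric research can exclude a child on safety grounds at visit 1 or 2, and the physical examination at both visits includes respiratory effort and lung auscultation.
- The first dose is followed by 30 minutes of observation.
- Treatment can be interrupted for viral upper-airway infection in subjects with asthma.
- Asthma exacerbations are events of special interest, which the DMC reviews.
- Asthma medication is recorded (11.8), and the SAP plans asthma-history tables (8.5), medication summaries (8.6) and FEV1 percent predicted by visit (6.9.3).

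Much of this stands. The safeguards are partial but real. The mild to moderate half of the statement is roughly supported by the E5 dose cap. No endpoint, estimand, power or error rate is affected.

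It does not answer the point. E16 and the examination set no standard for control, and with an estimated 75-80 sites individual discretion cannot guarantee that only well controlled asthma is enrolled. Observation, stopping rules and event review act after exposure. Medication and history tables do not yield a control category. Rewording 1.5 would make the sentence true but would not deliver the population it describes.

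**Conclusion.** The concern holds. Section 1.5 claims a property of the enrolled population that the eligibility list does not secure: 0 of 32 criteria test current asthma control, and the three asthma-specific ones leave an identifiable gap for symptomatic, under-treated children. Only general investigator discretion could close it.

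How many children this affects cannot be stated, because the documents give neither the share of subjects with asthma nor a control rate. The conclusion rests on two readings: that FEV1 at or above 70% predicted is compatible with symptomatic asthma, and that a discretionary criterion that does not name asthma is not a check of control. The change should be made because it is cheap and enforces what the sponsor already says it does. It does not threaten the efficacy conclusions. Confidence is medium.

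**What to change.** Add to section 4.2, beside E5 to E7, an exclusion for asthma that is not well controlled. The investigator would judge it from recent daytime and night symptoms, activity limitation and reliever use, for example using the GINA guideline that the protocol already uses for ICS doses.

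Check it at visits 1 and 2, with visit 2 deciding. That matches the timing of E5 to E7, which are tied to randomisation. It also avoids needless losses, since section 4.3.1 does not allow re-screening after this kind of failure. Visit 1 may be up to 26 weeks before visit 2, so a child whose treatment is stepped up after visit 1 could still qualify once the ICS dose has been unchanged for 4 weeks.

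Record the result in the eCRF and show it beside asthma status in the baseline table (SAP 8.4). If the criterion is not added, section 1.5 should at least claim no more than E5 to E7 enforce.

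The cost is one short assessment at two visits for children with asthma, one eCRF item, and some additional screen failures. Their number cannot be estimated from the documents, and letting visit 2 decide limits it.
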